
Revised the following exclusion criteria:
 
 • Amended laboratory abnormality parameters in exclusion criteria #2 • Changed estimated creatinine clearance (CrCl) per Cockcroft-Gault parameters for escalation stage • Added exclusion of patients that have used St. John’s wort within 3 weeks of study initiation • Consolidated exclusion criterion #7 into #5 • Changed exclusion criterion #9 to clarify prohibited drugs and clarify exclusionary window for patients that have used these drugs prior to study initiation • Added patients with interstitial lung disease to exclusion criterion #13 • Removed exclusion criterion #24 from the protocol body to align with the synopsis 
Added the following exclusion criteria:
 
 • #24 Ongoing psychiatric disorder, specifically patient with depression and/or suicidal tendencies • #25 Patients with pathological fractures, especially with unknown etiology 	
Section 5.1.2 Exclusion Criteria

Simplified drug labeling procedure to avoid conflicting information
	
Section 5.3.2 Drug Labeling

Clarified the HMPL-523 dosing window and administration with food
	
Section 5.3.4 Dosage, Administration, and Compliance

Description and Rationale for Change	Sections
Clarified eligibility criteria for post-trial access to HMPL-523	Section 5.3.5 Post-Trial Access to HMPL-523
Added reference http://medicine.iupui.edu/clinpharm/ddis/main-table	Section 5.5 Concomitant Therapy and Food
Changed ECG requirement from screening and pre-dose to one or the other	Section 5.6.10 Electrocardiogram
Added +/-7 day window to tumor assessments to align with NTF issued to sites previously	Section 5.6.12 Tumor and Response Evaluation
Clarified intent of laboratory assessments window prior to initiating HMPL-523 dosing	Section 5.6.9 Laboratory Assessments
Added parameters to align with EMA guidance	Section 5.8 Study/Site Discontinuation and Closure
Removed DLT notification “form” to align with NTF issued to sites previously	Section 6.2.4 Reporting of Dose-Limiting Toxicity
Added a new analysis population, the response evaluable set	Section 7.2 Analysis Population
Added text to the planned analysis for clarity	Section 7.3 Analysis Planned
Added description of pharmacodynamics assessments for certain patients at the sponsor’s discretion	Section 5.9 Assay Methods
Added section describing the biomarker analysis	Section 7.3.6 Biomarker Analysis (new section)

**MODIFICATION HISTORY**

[figure not shown]
CCI

A large black rectangular redaction box covers the majority of the page, obscuring the modification history table. The text "CCI" is visible in the top-left corner of this redacted area.

HMPL-523

CCI

A large black rectangular redaction box covers the majority of the page content. The text "CCI" is visible in the top-left corner of this redacted area.

HMPL-523

---

## 1. LIST OF ABBREVIATIONS

Abbreviation	Definition
AE	Adverse event
AESI	Adverse Events of Special Interest
ALT	Alanine aminotransferase
ALP	Alkaline phosphatase
ANC	Absolute neutrophil count
aPTT	Activated partial thromboplastin time
AST	Aspartate aminotransferase
ATC	Anatomical Therapeutic Chemical
BTK	Bruton tyrosine kinase
CBCL	Cutaneous B-cell lymphoma
CFB	Change from Baseline
CLL	Chronic lymphocytic leukemia
CR	Complete Response
CRi	Complete Response with Incomplete Marrow Recovery
CRF	Case report form
CTMS	Clinical trial management system
CT	Computer tomography
CTCAE	Common Terminology Criteria for Adverse Events
DLBCL	Diffuse Large B-cell Lymphoma
DEAS	DLT evaluable analysis set
DD	Drug Dictionary
DLT	Dose limiting toxicity
DMC	Data monitoring committee
DoR	Duration of response
ECG	Electrocardiogram
ECOG	Eastern cooperative oncology group
ENR	All patients enrolled set
FAS	Full analysis set
FL	Follicular lymphoma
IA	Interim analysis
INR	International normalized ratio
IPI	International prognostic Index
LDH	Lactate dehydrogenase
LLN	Lower limit of normal
LPL/WM	Lymphoplasmacytic lymphoma / waldenström's macroglobulinemia
LVEF	Left ventricular ejection fraction
MedDRA	Medical Dictionary for Regulatory Activities

HUTCHMED Ltd.

CONFIDENTIAL

HMPL-523

---

MR	Minor response
MRI	Magnetic resonance image
MTD	Maximum tolerated dose
MUGA	Multigated acquisition scan
MZL	Marginal zone lymphoma
NCI	National cancer institute
NA	Not applicable
ND	Not done
NE	Not evaluable
nPR	Nodular partial response
ORR	Objective response rate
PCFB	Percentage Change from Baseline
PD	Progressive disease
PFS	Progression free survival
PK	Pharmacokinetics
PSAS	Pharmacokinetics Analysis Set
PR	Partial response
PR-L	Partial Response with Lymphocytosis
PT	Prothrombin time
PTCL	Peripheral T-cell Lymphoma
QD	Once daily
QTc	Corrected QT interval
RES	Response Evaluable Set
RP2D	Recommended phase 2 dose
SAE	Serious adverse event
SAF	Safety analysis set
SAP	Statistical analysis plan
SD	Stable disease
SLL	Small lymphocytic lymphoma
SRC	Safety review committee
TEAE	Treatment emergent adverse events
TESAE	Treatment emergent serious adverse events
TTR	Time to response
ULN	Upper limit of normal
VGPR	Very good partial response
WHO	World health organization

---

Note: Standard units such as mg and mL as used in the text are not included in the abbreviations list.

HMPL-523

---

## 2. INTRODUCTION

This study is a two-stage, open-label, multicenter Phase 1 study to evaluate the safety, Pharmacokinetics (PK), and preliminary efficacy of HMPL-523 in patients with relapsed or refractory lymphoma who have exhausted approved therapy options. The study consists of two stages. Stage 1 is a dose escalation phase, in which a modified 3+3 design is applied for the dose escalation and to determinate the maximum tolerated dose (MTD) / recommended Phase II dose (RP2D). Stage 2 is a dose expansion stage, in which the safety, tolerability, PK, and preliminary efficacy of HMPL-523 at MTD/RP2D will be further evaluated in patients with relapsed, refractory, or resistant NHL.

The purpose of this Statistical Analysis Plan (SAP) is to provide a description of the statistical methods and conventions to be implemented in the presentation and analysis of efficacy and safety data from study 2018-523-00US1. This document is based on Protocol Amendment 5 dated 14Jun2024. It describes the data to be summarized and analyzed, including specifics of the statistical analyses to be performed. If circumstances arise during the study such that more appropriate analytic procedures become available, the SAP may be revised. This SAP supersedes the statistical considerations identified in the protocol; where considerations are substantially different, they will be identified. Any revisions to the SAP will be made and finalized prior to the final Database Lock (DBL), and any deviations from the SAP will be documented in the final Clinical Study Report (CSR).

The PK and pharmacodynamics analyses will be described in a separate analysis plan. All statistical analyses except for PK specific analyses will be performed by IQVIA Biostatistics.

## 3. STUDY OBJECTIVES

### 3.1. PRIMARY OBJECTIVE

The primary objectives are:

- To evaluate the safety and tolerability of HMPL-523 in patients with relapsed or refractory lymphoma in the dose escalation stage.
- To determine MTD/RP2D and characterize the dose-limiting toxicities (DLTs) associated with HMPL-523 in patients with relapsed or refractory lymphoma in the dose escalation stage.
- To evaluate the preliminary efficacy of HMPL-523 in patients with relapsed or refractory

HMPL-523

---

lymphoma in the dose expansion stage.

### **3.2. SECONDARY OBJECTIVES**

The secondary objectives are:

- To characterize the PK properties of HMPL-523 in patients with relapsed or refractory lymphoma in the dose escalation stage and the dose expansion stage.
- To evaluate the safety and tolerability of HMPL-523 at the MTD/RP2D in patients with relapsed or refractory lymphoma in the dose expansion stage.
- To evaluate the preliminary efficacy of HMPL-523 in patients with relapsed or refractory lymphoma in the dose escalation stage.

### **3.3. EXPLORATORY OBJECTIVES**

The exploratory objectives are:

- To evaluate the PK properties of the major metabolites of HMPL-523 in patients with relapsed or refractory lymphoma in the dose escalation and dose expansion stages.
- To explore biomarkers for progressive disease, predictive, and others (not exhaustive), including anti-tumor activities of HMPL-523.

HMPL-523

---

## 4. STUDY DESIGN

### 4.1. GENERAL DESCRIPTION

This is a Phase I, open-label, multicenter study of HMPL-523 administered orally to patients with relapsed or refractory lymphoma who have exhausted approved therapy options. The study consists of a dose escalation stage (Stage 1) and a dose expansion stage (Stage 2). Both stages include a screening period, a treatment period, and a follow-up period. The screening period starts when the patient has provided written informed consent and ends immediately prior to initiation of study drug administration on Day 1 of Cycle 1. The treatment period begins on Day 1 of Cycle 1 and concludes on the final day of study drug administration. The follow-up period begins at the end of treatment and continues until the patient experiences disease progression, starts a new anticancer therapy, or dies, or the sponsor has concluded the study.

As of (b) (4) no new patients were enrolled in the study. The study is now closed to enrollment. A total of 48 patients were enrolled in the dose-expansion portion at the time of enrollment closure.

#### 4.1.1. DOSE ESCALATION STAGE (STAGE 1)

In the dose escalation stage (Stage 1), a modified 3+3 design will be applied for dose escalation and MTD/RP2D determination, starting dosing from 100 mg QD orally. A cycle of study treatment will be defined as 28 days of continuous dosing.

For all patients in Stage 1, DLTs will be assessed during the DLT assessment window of 28 days (i.e., from Cycle 1 Day 1 [the day of first administration of treatment] through Cycle 1 Day 28). Patients who complete the DLT assessment window (Cycle 1 Days 1-28) and are deemed by the investigator to be benefiting from HMPL-523 treatment may continue with HMPL-523 treatment until disease progression, intolerable toxicity, at the investigator's discretion that the patient can no longer benefit from the study treatment, patient withdrawal from the study, the end of study, or death, whichever comes first.

The sample size for Stage 1 is based on the dose-escalation rules of the 3+3 design. The proposed dose escalation cohort include 6 groups: 100mg QD, 200 mg QD, 400 mg QD, 600 mg QD, 700 mg QD, and 800 mg QD.

Based on evaluation of data collected during the dose escalation phase, the RP2D has been determined to be 700 mg QD.

HMPL-523

To enhance the safety and integrity of the study, a Safety Review Committee (SRC) comprised of the sponsor's study team members (including medical monitor, safety monitor and others as may be deemed necessary), and the sites' principal investigators will convene to review all accumulated data for the study. The SRC will periodically convene following the completion of each dose level cohort and before enrollment may proceed to the next dose level.

#### **4.1.2. DOSE EXPANSION STAGE (STAGE 2)**

The safety, tolerability, PK, and preliminary efficacy of HMPL-523 at the MTD/RP2D, which has been determined to be 700 mg once daily, will be further evaluated in patients with relapsed or refractory non-Hodgkin's and Hodgkin's lymphomas.

Upon implementation of protocol amendment 5 and closure to enrolment, a total of 48 patients were enrolled in the dose-expansion portion. The last patient was enrolled on CCI .

### **4.2. SAMPLE SIZE DETERMINATION**

The sample size rationale for the study prior to closing for further enrollment is described below.

#### **4.2.1. STAGE 1: DOSE ESCALATION STAGE**

The sample size for Stage 1 was based on the dose-escalation rules of the 3 + 3 design. For a given AE with a true rate of 10%, 5%, or 1%, the probability of observing at least 1 such AE in a given cohort of 6 patients is 46.9%, 26.5%, and 5.8%, respectively.

#### **4.2.2. STAGE 2: DOSE EXPANSION STAGE**

The planned enrollment for Stage 2 was approximately 70 patients. The anticipated enrolment of 70 patients was to provide more robust safety data in the patient populations studied. For a given AE with a true incidence rate of 10%, 5%, or 1%, the probability of observing at least 1 such AE in 70 patients is 99.9%, 97.2%, and 50.5%, respectively.

### **4.3. SCHEDULE OF EVENTS**

Schedule of events can be found in [APPENDIX 1](#) of the protocol.

HMPL-523

---

## **5. PLANNED ANALYSES**

A soft lock for a data snapshot was performed followed by a preliminary evaluation of selected efficacy and safety endpoints to support a publication.

### **5.1. INTERIM ANALYSIS (IA)**

There was no planned IA for this study, however, additional analyses may have been conducted upon sponsor request for internal decision-making purposes, for example to provide information for a potential Phase 3 study design.

### **5.2. FINAL ANALYSIS**

All final, planned analyses identified in this SAP will be performed by IQVIA Biostatistics by following sponsor's authorization of this SAP prior to DBL for this study.

## **6. ANALYSIS SETS**

### **6.1. ALL PATIENTS ENROLLED SET [ENR]**

The ENR will contain all patients who provided informed consent for this study.

### **6.2. FULL ANALYSIS SET [FAS]**

The FAS is defined as all patients who received at least 1 dose of HMPL-523. The FAS will be used for the analysis of safety data and efficacy data (except Objective Response Rate [ORR], Time to Response [TTR], and Duration of Response [DoR]). Patients will be analyzed by their actual dose initially received. If patients were dose reduced during the study, all data will be summarized/analyzed based on the initial dose of study treatment received.

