Systemic exposures of HMPL-523 increased with dose up to 1000 mg QD on Day 1 and up to 800 mg QD on Day 15 and Day 28. The exposures at steady state appeared to drop off when dose increased from 800 mg QD to 1000 mg QD. The reason is unclear but may be related to the large between-subject PK variability (around 60% to 80%) in comparison to the small dose increment (25% increase in dose from 800 to 1000 mg). In the dose escalation stage, the highest geometric mean exposure was achieved following the 800 mg QD dose on Day 15 with AUC_{tau} of approximately 4890 h·ng/mL and C_{max} of approximately 385 ng/mL. In the dose expansion stage, the geometric mean AUC_{tau} and C_{max} on Day 28 were 3330 h·ng/mL and 246 ng/mL, respectively, at 800 mg QD, and 2710 h·ng/mL and 191 ng/mL, respectively, at 600 mg QD. The preliminary PK results showed that systemic exposure of HMPL-523 in Australian subjects was lower than that in Chinese subjects, but other PK characteristics in Chinese and Australian subjects were similar.

The plasma concentration of CCI [REDACTED] were monitored in this study (data on file). The mean ARs of area under the drug concentration-time curve over the dose interval at steady state ($AUC_{tau,ss}$) CCI [REDACTED] were 3.16 and 1.75, respectively, following multiple 100 to 1000 mg QD or 300 and 400 mg BID doses. The mean CCI [REDACTED] ratios of $AUC_{tau,ss}$ were approximately CCI [REDACTED] respectively. The mean

CCI

respectively.

Efficacy

As of 10 May 2020, in study 2015-523-00AU1, 61 patients had at least 1 post-baseline tumor assessment, and the objective response rate (ORR) in all enrolled patients was C%, with █ patients achieved CR, C patients achieved PR/partial response with lymphocytosis (PR-L), C patients achieved SD, C patients experienced progressive disease (PD), and 4 patients not evaluable for best overall response (BOR). CCI patients with FL (█ at 600 mg QD, █ at 800 mg QD, and █ at 400 mg BID) achieved CR, █ patients with CLL/SLL (█ at 800 mg QD, █ at 400 mg BID, and █ escalated from 100 mg QD to 400 mg QD) achieved PR/PR-L, █ patients with FL (█ at 600 mg QD, █ at 800 mg QD, and █ at 300 mg BID), █ patients with MZL (█ at 600 mg QD, █ at 800 mg QD), and 1 patient with low grade NHL (600 mg QD) achieved PR.

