4.2 Dose Escalation Stage (Stage 1)

Starting Dose and Rules for Dose Escalation

Dosing will begin at 100 mg QD. A cycle of study treatment will be defined as 28 days of continuous dosing. The modified 3 + 3 design will be applied for dose escalation and MTD determination to limit the number of patients being exposed to potentially ineffective or unsafe doses. The study will enroll 1 patient, and the patient will be treated for a 28-day cycle in the initial dose cohort. If there is no DLT and no more than 2 TEAEs of Common Terminology Criteria for Adverse Events (CTCAE) Grade ≥ 2 in the first treatment cycle, the study will be escalated to the next dose cohort and continue with the standard 3+3 design. Otherwise, the trial will revert to a standard 3+3 design from the initial dose cohort.

A minimum of 3 patients will be enrolled and observed for toxicity in each successive dose cohort after the initial dose cohort. If the 3 patients initially enrolled in a given dose cohort complete the DLT assessment window (Cycle 1, Days 1-28) without experiencing a DLT, 3 patients will be enrolled at the next higher dose level. If 2 or more of the initial 3 patients enrolled at any dose level experience a DLT during the DLT assessment window, the dose escalation will be halted. If 1 of the initial 3 patients enrolled at any dose level experiences a DLT during the DLT assessment window, additional patients will be enrolled at that dose level for a minimum of 6 evaluable patients for DLT. If a DLT is observed in 1 of the 6 evaluable patients at this dose level, dose escalation will proceed to the next pre-defined dose level. If DLTs are observed in 2 or more of the 6 evaluable patients at a given dose level, the dose escalation will be halted. If the dose escalation is completed due to 2 or more DLTs at a dose level and that dose level is $\geq 50\%$ higher than the previous dose level, then an intermediate dose level may be evaluated for toxicity in the same manner as described above. If the dose level is $<50\%$ higher than the previous dose level, in which only 3 DLT evaluable patients were enrolled, 3 additional patients will be enrolled at that dose level to comprise 6 DLT evaluable patients.

See [Table 1](#) below for the proposed dose escalation scheme.

Table 1 Proposed Dose Escalation Scheme

Cohort	Dose	Route of Administration
1	100 mg QD	Orally, with water, after meal
2	200 mg QD	Orally, with water, after meal
3	400 mg QD	Orally, with water, after meal

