4.3 Inpatient Dose Escalation

Inpatient dose escalation to a higher dose level may be permitted by the sponsor, provided that the current dose level the patient is on has been cleared of DLT (safe and tolerable), and the higher dose level cohort being considered also has been cleared of DLT (safe and tolerable), prior to the start of that inpatient dose escalation.

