4.4.2 Definition of Dose-Limiting Toxicity Evaluable Patient

For decisions on dose escalation, each dose cohort shall present protocol-required number of DLT evaluable patients. A patient is DLT evaluable if he/she meets the following criteria:

- Has received at least 75% of the assigned dose of study medication during the DLT assessment window

OR

- Has not completed DLT assessment period due to a DLT

Patients who are not DLT evaluable in a dose cohort will be replaced to guarantee the protocol required number of DLT evaluable patients for dose escalation evaluations.

4.4.3 Dosing Beyond Cycle 1

Patients who complete the DLT assessment window (Cycle 1 Days 1-28) and are deemed by the investigator to be benefiting from treatment with HMPL-523 may continue treatment with HMPL-523 until disease progression, intolerable toxicity, at investigator's assessment that the patient is no longer benefiting from the study treatment, patient withdrawal from the study, the end of the study, or death. Conversely, if in the opinion of the attending principal investigator the patient may have clinical benefit from a higher dose, then, at the request of the principal investigator and with the approval of the sponsor, the patient may be able to participate in inpatient dose escalation (Section 4.3). If the study is terminated or ends before a patient reaches any of these endpoints, refer to Section 5.3.5.

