4.8.2 Secondary Safety Outcome Measures

- Incidence of TEAEs by NCI CTCAE v5.0 grade and associated dose of HMPL-523
- Incidence of Grade 3 and 4 abnormalities in safety-related laboratory parameters and associated dose of HMPL-523
- Incidence of TEAEs leading to HMPL-523 dose interruption, reduction, or treatment discontinuation

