## 15. STUDY MEDICATION EXPOSURE AND COMPLIANCE

Exposure to study medication in days will be summarized based on the FAS.

The date of first study medication administration will be taken from the "HMPL-523 Treatment" eCRF form. The date of last study medication will be taken from the last study medication administration date.

Study drug interruptions, compliance, and dose changes are not taken into account for duration of exposure.

The following study medication administration summaries will be reported for this study:

- Number of cycles: the number of cycles in which the patient took any dose of study medication.
- Total duration exposure (months):

$$\text{Total duration of treatment (months)} = \left( \frac{\text{date of last dose} - \text{date of first dose} + 1}{30.4375} \right)$$

It will be summarized as continuous variables and also categorized into groups as below:

- < 6 months exposure
  - $\geq 6$  to < 12 months exposure
  - $\geq 12$  months exposure
- Actual duration of study treatment (months):

Actual duration of study treatment is defined as the total number of months on the study medication during the treatment phase (excluding the periods of dose discontinuation or dose interruptions).

- Cumulative dose (mg):

Cumulative dose (mg) is defined as the sum of the total doses patient actually received during an exposure period.

HMPL-523

- Dose intensity (mg/day):

$$\text{Dose intensity (mg/day)} = \left( \frac{\text{Cumulative dose (mg)}}{\text{total treatment exposure(days)}} \right)$$

- Relative dose intensity (%):

$$\text{Relative dose intensity (\%)} = \left( \frac{\text{dose intensity (mg/day)}}{\text{planned dose intensity(mg/day)}} \right) * 100$$

The planned dose intensity is defined in the protocol for each cohort: 100mg/day, 200mg/day, 400 mg/day, 600 mg/day, 700 mg/day, and 800 mg/day.

It will be summarized as continuous variables and also categorized into groups as below:

- < 50%
- 50% - <70%
- 70% - <90%
- 90% - <110%
- $\geq$ 110%

The number and percentage of patients with any dose modification will be presented. Dose modification will be further characterized by presenting the numbers and percentages of patients with any dose reduction, dose escalation and dose interruption. Reasons for dose adjustments will be summarized as well.

Details of study treatment administration will be included in patient listings.

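### If a Stage 1 patient moved to a higher dose, the SAP tabulates later toxicity and response under the lower starting dose, and no output shows the dose at onset

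*SAP*

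**What the plan says.** Protocol 4.3 states: "Inpatient dose escalation to a higher dose level may be permitted by the sponsor". The condition is that both the patient's current level and the higher level have been cleared of DLT. The word used there is inpatient, but the context shows that escalation within the same patient is meant. Protocol 4.4.3, on dosing beyond Cycle 1, adds that at the investigator's request and with sponsor approval "the patient may be able to participate in inpatient dose escalation".

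SAP 6.2 sets the attribution rule for the Full Analysis Set: "Patients will be analyzed by their actual dose initially received". The next sentence deals with one kind of dose change only: "If patients were dose reduced during the study, all data will be summarized/analyzed based on the initial dose of study treatment received". Escalation is not mentioned. SAP 15 does provide for it, counting patients with "any dose reduction, dose escalation and dose interruption" and including a relative dose intensity category of 110% or more.

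Stage 1 results are then laid out by dose. SAP 8 says so generally, SAP 17.2.1 for TEAEs, SAP 17.5 for ECGs and SAP 16 for efficacy (by dose cohort). SAP Appendix 3 puts all summaries under the assigned dose level. Protocol 4.8.2 defines the secondary safety outcome as "Incidence of TEAEs by NCI CTCAE v5.0 grade and associated dose of HMPL-523", and words the Grade 3 and 4 laboratory outcome in the same way.

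**The concern.** The protocol permits a dose change that the SAP's attribution rule does not reflect. An adverse event, a Grade 3 laboratory value or a QTcF increase that begins while a patient takes 400 mg would appear in the 100 mg column if that patient started at 100 mg, and would be missing from the 400 mg column. The lower dose then looks more toxic than it was, and the higher dose less so. A first response reached after escalation is misplaced in the same way.

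What is at stake is the descriptive picture of toxicity and activity across Stage 1 dose levels. Stage 1 cohorts are very small, so one misplaced patient can change how a row reads.

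**Working it through.** The plan gives no figure on this point, so there is none to reproduce. The check has two parts: tracing the rule through the outputs, and illustrating its effect.

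**Tracing the rule**

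1. *Can escalation happen?* Yes. Protocol 4.3 and 4.4.3 permit it after the 28-day DLT window.
2. *Which dose do safety data and PFS go under?* They use the FAS. The general sentence in SAP 6.2 has no exception for escalation, so they go under the starting dose.
3. *Which dose do ORR, TTR and DoR go under?* SAP 6.2 excludes these from the FAS; they use the Response Evaluable Set. SAP 6.3 gives that set no attribution rule. The dose comes from SAP 16 (dose cohort) and Appendix 3 (assigned dose level). A cohort is the one a patient entered, so the result is again the starting dose. The assigned dose level could, however, be read as first or current assignment.
4. *Does any output use dose at onset or at response?* No. Escalation appears only as a count with reasons in SAP 15 and in the patient listings of dosing.
5. *Does the result fit the protocol outcome?* Protocol 4.8.2 links TEAEs and Grade 3 and 4 laboratory abnormalities to the associated dose. For an event that starts after escalation, the starting dose is not the natural reading.
6. *Are DLTs affected?* No. The window is Cycle 1 Days 1 to 28, and escalation is described for dosing beyond Cycle 1.

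**Illustrating the effect**

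Assumption: one escalated patient has one event, or one first response, at the higher dose, and nobody else in the starting cohort has any. Cohort sizes come from Protocol 4.2: "The study will enroll 1 patient, and the patient will be treated for a 28-day cycle in the initial dose cohort", then at least 3 per cohort, and at least 6 evaluable if a DLT is seen. Intervals are 95% Clopper-Pearson, the SAP's method for percentages. For 0/n the upper limit is 1 − 0.025^(1/n); for n = 3 this is 1 − 0.025^(1/3) = 70.8%.

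| Starting cohort | Events at the starting dose itself | As tabulated under SAP 6.2 | Shift |
|---|---|---|---|
| 1 | 0/1 (0 to 97.5%) | 1/1 (2.5 to 100%) | 100 points |
| 3 | 0/3 (0 to 70.8%) | 1/3 (0.8 to 90.6%) | 33.3 points |
| 6 | 0/6 (0 to 45.9%) | 1/6 (0.4 to 64.1%) | 16.7 points |

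**How much exposure can sit at another dose**

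SAP 15 defines relative dose intensity as dose intensity divided by the cohort's planned dose intensity, times 100. Assume six equal cycles, no missed doses, and escalation after the first cycle:

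- 100 to 200 mg: (100 × 1 + 200 × 5) / 6 = 183.3 mg/day, or 183% of 100 mg/day.
- 100 to 400 mg: (100 × 1 + 400 × 5) / 6 = 350 mg/day, or 350%.

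In both cases five of the six cycles are taken at a dose other than the one the tables show.

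**The case against.** Several points on the other side stand.

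- **No passage shows that anyone escalated.** A count row and a 110% category provide for escalation; they do not show that it occurred. Appendix 18 records Protocol 4.3 as a new section in Amendment 1 (April 2020), while Protocol 4.1 dates the opening of recruitment to February 2019. Whether the earliest patients could have escalated is unknown.
- **Analysis by starting dose is legitimate.** It gives one stable denominator and follows the protocol's instruction in 7.3.3 and 7.3.5 to summarise Stage 1 by dose level. The phrase associated dose is not defined, so reading it as dose at onset is an interpretation, though the natural one.
- **Listings allow reconstruction.** Dosing, adverse events, laboratory values, ECGs and tumour assessments are all listed, and in cohorts this small a reader could work out the dose at an event. The summary tables would still mislead anyone who reads only those.
- **Stopping best overall response at escalation would be wrong.** Protocol 4.8.4 and SAP 16.1.1 define it from the start of treatment until progression or further anticancer therapy.

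Three stronger readings are tempting but unsupported. A reader might infer that the primary Stage 1 safety result is distorted; the primary safety outcome is DLT incidence (Protocol 4.8.1), which is untouched. A reader might infer that the basis for 700 mg is weakened; Protocol 4.4.5 shows that the RP2D is already determined, and the layout of final tables cannot alter it. A reader might apply the quoted FAS sentence to ORR; it does not govern ORR, and the link for response runs through SAP 16 and Appendix 3.

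The protocol's summary of the Australian study describes a responder as "escalated from 100 mg QD to 400 mg QD". This is background on another study, and shows only that such labelling has been used.

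**Conclusion.** The concern holds within limits. Taken as written, the SAP places post-escalation TEAEs and Grade 3 and 4 laboratory abnormalities from Stage 1 under a dose the patient was no longer taking, which does not fit the protocol's outcomes by associated dose. ECG abnormalities and response by dose cohort are misplaced in the same way, though Protocol 4.8 does not tie those to an associated dose. The SAP is silent on escalation although its own exposure section provides for it.

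The actual size is unknown and may be zero, because the documents do not give the number of escalated patients. If there is one such patient with one event, the shift is 16.7 points in a cohort of 6, 33.3 points in a cohort of 3, and the whole row in a cohort of 1. DLT counts, the MTD, the RP2D and the Stage 2 summaries by malignancy are not affected. The finding bears on the descriptive Stage 1 dose pattern, and is worth correcting because the correction is small.

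**What to change.** In SAP 6.2, 16 and 17:

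1. State explicitly how patients who escalate are handled, for both the FAS and the Response Evaluable Set, and align Appendix 3 with that wording.
2. Keep the starting-dose tables and the protocol definition of best overall response.
3. Add a supplementary Stage 1 table of TEAEs, Grade 3 and 4 laboratory abnormalities and ECG abnormalities by the dose being taken at onset. Use the patients and exposure time at each dose as denominators.
4. In the Stage 1 efficacy tables and listings, flag any response first reached after escalation and give the dose at that time.

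The cost is SAP wording, one derived variable for dose at onset, and one extra table. The dosing records are already collected, and SAP 2 allows revision before final database lock. If nobody escalated, the table adds nothing and a sentence can say so. An escalated patient will appear in more than one column of the supplementary table. Events at the higher dose will come from patients selected for tolerating the lower one, and may include carry-over. The table is therefore descriptive and should be labelled as such.
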